10. INTERIM ANALYSES

An interim analysis was planned per Protocol Section 10.5, but due to early study termination, the interim analysis was not conducted.

11. CHANGES AND MODIFICATIONS TO THE ANALYSIS PLAN

All versions of the SAP are listed in Table 6.

Table 6: Statistical Analysis Plan Versions

SAP Version	Date
Original	09 FEB 2022
Amendment 1	01 DEC 2023

11.1. Changes to Protocol-Defined Analyses

The analysis of potential Hy's law events has been changed from the Protocol version to a newly created company standard of assessing potential drug-induced liver injuries.

The ECG variable QTcF was updated to QTc to correct a typo in the statistics section of the Protocol. RR was also removed since it was not mentioned in Protocol Section 8.3.5.

The number of responses needed at the final analysis was increased by 1 for the HCC and RCC cohorts in order to make the number higher than the number required for the interim.

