10.3. Level of Significance

Formal statistical tests for the primary endpoint will be performed for each cohort that control Type I error at \leq 1-sided 5% for each cohort. Parameters for other secondary [REDACTED] endpoints will be estimated using 95% CIs.

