10.5. Interim Analysis

A safety/efficacy run-in analysis is planned when up to 15 participants in select disease-specific cohorts of each dose level are evaluable for response using the RECIST evaluable population. The Type I error inflation would only require at most a 1-participant increase to the sample size for each cohort shown in [Table 20](#) in order to maintain the level at 0.05; therefore, the impact of this run-in is minimal. Safety and efficacy will be assessed to determine whether to continue with the study or stop after the run-in analysis. With 15 participants, there is approximately 91.3% probability of observing at least an objective response if the underlying response rate is 15%.

After passing the run-in, the study will proceed according to the group sequential rules in [Table 24](#). Nonbinding interim futility analyses are planned after approximately 50% of the participants in each disease-specific cohort of each dose level are evaluable for response using the RECIST evaluable population. Information from all cohorts and other emerging data will determine whether to pause or stop recruitment in any single cohort. The Hwang-Shih-DeCani ([Hwang et al 1990](#)) beta-spending function with parameter -1 will be used to determine the futility bound for all cohorts, and alpha-spending function with parameter -4 will be used to determine the efficacy bound for all cohorts except for melanoma, which used parameter -1 because lower values did not achieve at least 80% power. [Table 24](#) presents the planned nonbinding futility and efficacy boundaries for the interim and final analyses.

Table 24: Group Sequential Rules for Interim and Final Analysis

Tumor Type (Cohort)	Futility Boundary for ORR at Planned Interim Analysis	Efficacy Boundary for ORR at Planned Interim Analysis	Efficacy Boundary for ORR at Final Analysis
NSCLC	< 4/16 = 25%	≥ 8/16 = 50%	≥ 11/32 = 34%
UC	< 3/12 = 25%	≥ 7/12 = 58%	≥ 10/25 = 40%
HCC	< 2/21 = 10%	≥ 6/21 = 29%	≥ 6/42 = 14%
RCC	< 1/11 = 9%	≥ 4/11 = 36%	≥ 4/23 = 17%
Melanoma	< 2/15 = 13%	≥ 6/15 = 40%	≥ 8/30 = 27%

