3.2. Control of Type I Error

Not applicable.

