3.3. Sample Size Considerations

The number of participants based on a group sequential design with 1 interim per cohort at approximately 50% information using a Hwang-Shih-DeCani (1990) spending function has been determined independently for each disease-specific cohort (irrespective of dose level) and can be found in Table 2. The target ORR (p₁) for each cohort is based on published clinical experience with a reference PD-1 inhibitor (El-Khoueiry et al 2017, Keytruda 2018, Mok et al 2019, Motzer et al 2015, Reck et al 2016, Robert et al 2015). The target ORR (p₁) for the NSCLC cohort was calculated by combining 2 different studies (Mok et al 2019, Reck et al 2016). The null ORR (p₀) for the melanoma and RCC cohorts is based on the control arm ORRs in the reference studies. For the NSCLC, UC, and HCC cohorts, the null ORR (p₀) was selected to be the p₀ that creates a test with a rejection region that begins with the lower CI bound of the reference PD-1 inhibitors. The sample size for each cohort provides approximately 80% power and 5% 1-sided Type I error.

Table 2: Sample Size per Cohort

	ORR		
Tumor Type (Cohort)	$\mathbf{p_0}$	p_1	Sample Size
NSCLC	18.0%	41.1%	32
UC	20.0%	47.0%	25
НСС	6.0%	20.0%	42
RCC	5.0%	25.0%	23
Melanoma	11.9%	32.9%	30

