7.1. Efficacy Hypotheses

Not applicable.

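### SAP 3.3 still states about 80% power for every cohort, but with the final response counts raised in SAP 11.1 exact power is about 75% for HCC and 72% for RCC

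*SAP*

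**What the plan says.** SAP 3.3 describes a "group sequential design with 1 interim per cohort at approximately 50% information" and states: "The sample size for each cohort provides approximately 80% power and 5% 1-sided Type I error". Its Table 2 repeats the inputs of Protocol Table 20. For HCC the null response rate is 6%, the target 20% and N 42; for RCC they are 5%, 25% and 23.

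Protocol Table 24 gives the boundaries. For HCC and RCC the final efficacy count equals the interim efficacy count: 6/21 then 6/42, and 4/11 then 4/23. SAP 11.1 addresses this: "The number of responses needed at the final analysis was increased by 1 for the HCC and RCC cohorts", the reason given being that the final number should exceed the interim number. The SAP prints no boundary table and gives no revised power.

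Protocol 10.5 also explains the choice of alpha-spending parameter for melanoma, "which used parameter -1 because lower values did not achieve at least 80% power". Protocol 10.3 sets the error limit: "Formal statistical tests for the primary endpoint will be performed for each cohort that control Type I error at" no more than one-sided 5%.

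**The concern.** Raising a final success count at fixed N makes success harder to reach, so both power and Type I error must fall. In cohorts of 23 and 42 participants one response is a large step. SAP 11.1 took that step in two cohorts while SAP 3.3 kept the same sample sizes and the same power statement. Unless Table 24 had enough slack to absorb the change, SAP 3.3 describes a better-powered design than the one the SAP adopts. A study report that takes its design description from SAP 3.3 would repeat the overstatement.

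**Working it through.** **Inputs**

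| | HCC | RCC | Source |
|---|---|---|---|
| Null rate p0, target rate p1 | 6%, 20% | 5%, 25% | Protocol Table 20, SAP Table 2 |
| Interim n1, total N | 21, 42 | 11, 23 | Protocol Table 24 |
| Interim futility | fewer than 2 | fewer than 1 | Protocol Table 24 |
| Interim efficacy e | at least 6 | at least 4 | Protocol Table 24 |
| Final count r, Protocol | at least 6 | at least 4 | Protocol Table 24 |
| Final count r, amended | at least 7 | at least 5 | Table 24 plus 1 (SAP 11.1) |

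The test is exact binomial (Protocol 10.4.1.1).

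**Formula.** Let X1 be the responses among the first n1 participants and X2 the responses among the remaining N − n1. Then

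Power = P(X1 ≥ e) + Σ P(X1 = x) · P(X2 ≥ r − x),

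evaluated at p1. The sum runs over interim counts x that stop for neither futility nor efficacy. If the nonbinding futility rule is ignored, it starts at x = 0. Type I error is the same expression at p0.

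**Step 1: Protocol counts, futility followed**

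- HCC, 6/42: 0.2307 + (0.1211 × 0.6296 + 0.1917 × 0.8213 + 0.2156 × 0.9424 + 0.1833 × 0.9908) = 0.2307 + 0.6184 = **84.9%**
- RCC, 4/23: 0.2867 + (0.1549 × 0.6093 + 0.2581 × 0.8416 + 0.2581 × 0.9683) = 0.2867 + 0.5615 = **84.8%**
- The other three cohorts by the same method: NSCLC 81.7%, UC 81.3%, melanoma 82.1%.

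All five cohorts therefore exceed 80% under Table 24.

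**Step 2: amended counts, futility followed**

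Only the second-stage requirement changes; the interim terms are the same.

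- HCC, 7/42: 0.2307 + (0.1211 × 0.4140 + 0.1917 × 0.6296 + 0.2156 × 0.8213 + 0.1833 × 0.9424) = 0.2307 + 0.5206 = **75.1%**
- RCC, 5/23: 0.2867 + (0.1549 × 0.3512 + 0.2581 × 0.6093 + 0.2581 × 0.8416) = 0.2867 + 0.4289 = **71.6%**

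**Step 3: sensitivity to the futility convention and the interim**

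| Rule | Power, futility followed | Power, futility ignored | Power, no interim | Type I error, followed / ignored |
|---|---|---|---|---|
| HCC 6/42 | 84.9% | 87.1% | 87.1% | 3.5% / 3.8% |
| HCC 7/42 | 75.1% | 76.3% | 76.2% | 1.2% / 1.2% |
| RCC 4/23 | 84.8% | 86.3% | 86.3% | 2.5% / 2.6% |
| RCC 5/23 | 71.6% | 72.2% | 71.7% | 0.6% / 0.6% |

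No convention brings either cohort back to 80% at the amended count. Placing the RCC interim at 12 rather than 11 gives at most 72.5%.

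**Step 4: size of the gap**

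With the interim rules held fixed and the amended final counts:

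- HCC: N = 44 gives 78.9% with futility followed (80.5% ignored), and N = 45 gives 80.5% followed. The stated N is 42.
- RCC: N = 25 gives 77.8% followed (78.9% ignored), and N = 26 gives 80.5% followed (81.8% ignored). The stated N is 23.
- At the stated N, 80% power is reached at a true response rate of 21.1% for HCC (20.8% ignored) and 27.6% for RCC (27.4% ignored), against targets of 20% and 25%.

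**The case against.** The arithmetic is not in dispute; the weight put on it can be. Five points deserve an answer.

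- **The power claim is only approximate.** HCC sits 5 to 7 points above 80% at the Protocol count and 4 to 5 points below it at the amended one, and one response moves HCC power by about 10 points, so no count lands close to 80%. This has force for HCC taken alone. It does not cover RCC, where the chance of missing the target effect is about 28% rather than 20%. A power claim is also normally read as what the design delivers, so overshoot and shortfall are not equivalent.
- **80% is not stated as a floor for every cohort.** The Protocol 10.5 remark concerns melanoma only. That is correct as to wording. It still shows how the designers judged acceptable power, and all five cohorts clear 80% under Table 24. The shortfall appears only with the SAP 11.1 change.
- **SAP 3.3 may simply record the planning basis, and SAP 11.1 discloses the change.** SAP 11.1 discloses the count but not its cost, and nothing in SAP 3.3 says that its power refers to superseded boundaries.
- **The amended counts are not printed.** They are inferred, but SAP 11.1 lists changes from the Protocol, so Table 24 plus 1 is the natural reading and fits the reason given.
- **The rule is no longer in use.** This stands. The SAP marks "3.2. Control of Type I Error" and "7.1. Efficacy Hypotheses" as not applicable, and states that "due to early study termination, the interim analysis was not conducted". It limits the consequence but does not make the power statement correct.

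**Conclusion.** The concern holds, at minor severity. At the amended final counts, power is about 75% to 76% for HCC and about 72% for RCC, not about 80%. The loss from the Table 24 rule is roughly 10 to 11 points for HCC and 13 to 14 points for RCC. RCC is the firm case and HCC the smaller one.

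Only the power statement is wrong. Type I error falls to about 1.2% and 0.6%, within the Protocol 10.3 limit, and the stricter final count is a disclosed and conservative choice. The other three cohorts are unaffected. Because the study ended early with minimal enrollment and the SAP plans no hypothesis test, no analysis or result changes.

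The figures assume that the amended counts are 7/42 and 5/23, that the interim rules are those of Table 24, and that interims fall exactly at 21 and 11 participants. The run-in in up to 15 participants has no numeric stopping rule and is not modelled; at fixed boundaries and N, stopping there could only lower power further.

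**What to change.** Add to SAP 3.3, or to the design description in the clinical study report:

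> The power of approximately 80% refers to the boundaries in Protocol Table 24. With the final counts in Section 11.1 (7/42 for HCC, 5/23 for RCC), exact power is about 75% for HCC and 72% for RCC if the nonbinding futility rule is followed (76% and 72% if it is not), with one-sided Type I error of about 1.2% and 0.6%.

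Leave the SAP 11.1 entry as it stands. The cost is two sentences. No participants, analyses, tables or listings are affected; the only price is that two stated powers become less favourable.

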11.2. Changes to the Statistical Analysis Plan

11.2.1. Original to Amendment 1

Modifications were made to the original SAP to streamline analyses for a synoptic CSR, as this study was terminated early with minimal enrollment.

APPENDIX A. PLANNED TABLES AND LISTINGS

This appendix provides a list of the planned tables and listings for the CSR. Standard tables will follow the conventions in the standard safety tables. Shells are provided for nonstandard tables in a separate document. In-text tables are identical in structure and content as appendix tables but follow a rich text format.

The list of tables and listings and the shells are to be used as guidelines. Modifications of the list or shells that do not otherwise affect the nature of the analysis will not warrant an amendment to the SAP.

Tables

Table No.	Title	Population	Standard
Baseline ar	nd Demographic Characteristics		•
1.1.1	Analysis Populations	FAS	X
1.1.2	Summary of Participant Disposition	FAS	X
1.1.3	Summary of Number of Participants Enrolled by Country and Site	FAS	X
1.1.4	Summary of Important Protocol Deviations	FAS	X
1.2.1	Summary of Demographics and Baseline Characteristics	FAS	X
1.3.1	Summary of Baseline Disease Characteristics	FAS	X
Efficacy			
2.3.1	Summary of Best Overall Response per RECIST v1.1	FAS	
Safety			
3.1.1	Summary of Exposure and Duration of Exposure to INCB086550	Safety	X
3.1.2	Summary of Study Drug Compliance	Safety	X
3.2.1	Overall Summary of Treatment-Emergent Adverse Events	Safety	X
3.2.1.1	Overall Summary of Sponsor-Defined Immune-Related Adverse Events	Safety	X
3.2.2	Summary of Treatment-Emergent Adverse Events by MedDRA System Organ Class and Preferred Term	Safety	X
3.2.3	Summary of Treatment-Emergent Adverse Events by MedDRA Preferred Term in Decreasing Order of Frequency	Safety	X
3.2.4	Summary of Serious Treatment-Emergent Adverse Events by MedDRA System Organ Class and Preferred Term	Safety	X
3.2.5	Summary of Serious Treatment-Related Treatment-Emergent Adverse Events by MedDRA Preferred Term in Decreasing Order of Frequency	Safety	X
3.2.6	Summary of Treatment-Emergent Adverse Events With a Fatal Outcome by MedDRA System Organ Class and Preferred Term	Safety	X
3.2.7	Summary of Treatment-Emergent Adverse Events Leading to Discontinuation of INCB086550 by MedDRA System Organ Class and Preferred Term	Safety	X
3.2.8	Summary of Sponsor-Defined Immune-Related Adverse Events by Category and MedDRA Preferred Term	Safety	X
3.2.9	Summary of Treatment-Emergent Adverse Events Leading to Dose Modification of INCB086550 by MedDRA System Organ Class and Preferred Term	Safety	
3.3.3.1	Shift Summary of Hematology Laboratory Values in CTCAE Grade – to the Worst Abnormal Value	Safety	X
3.3.3.2	Shift Summary of Chemistry Laboratory Values in CTCAE Grade – to the Worst Abnormal Value	Safety	X

Listings

Listing No.	Title	
2.1.1	Participant Enrollment and Disposition Status	
2.1.1.1	Deaths	
2.1.2	Participant Inclusion and Exclusion Criteria Violations	
2.2.1	Important Protocol Deviations	
2.3.1	Analysis Populations	
2.4.1	Demographic and Baseline Characteristics	
2.4.2	Disease History	
2.4.3	Prior Anticancer Radiation Treatment	
2.4.4	Prior Systemic Anticancer Therapy	
2.4.5	Prior Anticancer Surgery or Surgical Procedure	
2.4.6	Medical History	
2.4.7	Prior and Concomitant Medication	
2.4.8	ECOG Performance Status	
2.5.1	Study Drug Compliance	
2.5.2	Study Drug Administration	
2.6.1	Investigator-Reported Response Assessment per RECIST v1.1	
2.6.2	Duration of Response per RECIST v1.1	
2.6.3	Response Assessment: Target Lesions	
2.6.4	Response Assessment: Nontarget Lesions	
2.6.5	Response Assessment: New Lesions	
2.6.6	Bone Scan Results	
2.7.1	Adverse Events	
2.7.2	Serious Adverse Events	
2.7.3	Fatal Adverse Events	
2.7.4	Adverse Events Leading to Interruption, Reduction, or Discontinuation of INCB086550	
2.7.5	Sponsor-Defined Immune-Related Adverse Events	
2.8.1.1	Clinical Laboratory Values – Hematology	
2.8.1.2	Clinical Laboratory Values – Chemistry	
2.8.1.3	Clinical Laboratory Values – Endocrine Function	
2.8.1.4	Potential Drug-Induced Liver Injuries
